Visits 5 – 8 (Weeks 4, 8, 12 and 18)

Subjects will attend the site for safety, PK and efficacy assessments.

Imaging Sub-Study

Subjects participating in the imaging sub-study will also undergo an MRI procedure on or immediately following Visit 7 (Week 12). All safety, PK and efficacy assessments will be performed prior to performing the MRI.

Visit 9 – Week 24 (End-of-Study or Early Exit Visit)

Subjects will attend the site for final safety, PK and efficacy assessments and will return any unused rescue medication, and their ePRO device.

Imaging Sub-Study

Subjects participating in the imaging sub-study will undergo an MRI procedure on or immediately following Visit 9 or the early exit visit. All safety, PK and efficacy assessments will be performed prior to undergoing MRI.

If a subject participating in the imaging sub-study exits the main study early, an early exit visit will be performed, and an early exit MRI acquired on or immediately following the visit. If the MRI is within 2 months of the previous MRI scan, then an MRI does not need to be performed, except in the case that the previous MRI was performed prior to dosing and the early exit MRI will be the only MRI collected post treatment administration. The early exit MRI will be conducted in this instance.

	
Visit 10 – Week 52 (for Imaging Sub-Study Only)
 
Only subjects participating in the optional imaging sub-study will perform Visit 10.
 
After Visit 9, no efficacy assessments, PK, or safety assessments apart from AE recording will be performed. Subjects will not be required to refrain from any medications/procedures after Visit 9. The subject will be treated as per standard of care by their physician during this time.
 
At Visit 10 AEs and concomitant medications/procedures will be collected for the timeframe between Visit 9 and 10 to capture any changes in the subject's health status. Eligibility to conduct imaging will be reviewed based on MRI-sub-study exclusion criteria. If the subject remains eligible to undergo the final MRI based on these criteria and has a negative result on a urine pregnancy test (for females of childbearing potential) they may proceed to have the final MRI scan.

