Sample Size	
A sample size of approximately 240 completed subjects (120 per arm) is estimated to provide approximately 80% power (at a 2-sided, 5% significance level) to detect a 0.8-point difference in WOMAC Pain subscale score (on a 0-10 scale) between EP-104IAR and vehicle (assuming a standard deviation of 2.2).
 
Assuming a 20% drop-out rate over the course of the study, approximately 300 subjects will be randomized and dosed.
 
Imaging Sub-Study
 
As this is an exploratory data collection, no power calculations have been considered.

Statistical Methods	
Efficacy Analyses
 
The primary efficacy endpoint is the difference in change from baseline between EP-104IAR and vehicle in WOMAC Pain at Week 12. The primary analysis will be performed in the ITT population.
 
Change from individual pre-dose baseline WOMAC Pain will be fit to a mixed-effects for repeated measures model using all available data from the ITT population. This model will contain fixed effects terms for site; individual baseline WOMAC Pain; and the treatment-by-week interaction, where treatment and week are both treated as categorical variables; and a random per-patient intercept. An unstructured residual covariance matrix at the patient level will initially be fit; if this model fails to numerically converge, a compound symmetry structure will be used. No missing data imputation will be included in this model. Inferential results will be produced for the difference between EP-104IAR and vehicle at Week 12.
 
Key secondary endpoints will be analyzed using analogous methods. A step-down hierarchical testing procedure will be used, at the 5% level, where each endpoint may only be formally assessed inferentially if all prior endpoints were statistically significant at the 5% level.
 
Additional secondary and exploratory analyses, and covariate analyses, will also be conducted where appropriate (see Section 11.7.3).
 
Safety and Pharmacodynamic Analyses
 
 • Safety data (safety labs, cortisol, physical exams, knee exams, vital signs, etc.) will be summarized by treatment using standard summary statistics for both raw data and change from baseline. • Treatment-emergent adverse events (TEAEs) will be summarized by treatment.

- Impact on hypothalamic-pituitary-adrenal axis (ACTH stimulation test results) will be summarized by treatment using standard summary statistics.

Pharmacokinetic Analyses

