11.7 Efficacy Evaluations

11.7.1 Primary

The primary efficacy endpoint is the difference in change from baseline between EP-104IAR and vehicle in WOMAC Pain at Week 12, in the ITT population.

Baseline WOMAC Pain will be calculated at the individual level and is defined as the average of three measurements; 2 measurements during the Washout and Baseline Period and 1 at Visit 2 (pre-dose). Change from individual pre-dose baseline will then be calculated for each post-dosing weekly assessment from Week 1 through Week 24. A mixed-effects model for repeated measures (MMRM) model will then be fit to the change from baseline data for all subjects in the ITT population, including fixed effects terms for:

site (potentially grouped, a classification that will be made as part of the blind review process and documented in the SAP prior to formal study unblinding); individual baseline WOMAC Pain; and the treatment-by-week interaction, where treatment and week are both defined as categorical variables. A random per-patient intercept will also be included. An unstructured covariance matrix at the patient level will initially be fit; if this model fails to converge numerically, a compound symmetry structure will be used.

No imputation of missing data will be performed for this analysis; the MMRM model allows handling of missing data under a suitable set of missing data assumptions. If blinded data review indicates that those assumptions appear not to be met, or there is a non-negligible degree of missingness, suitable alternative modeling approaches will be detailed in the SAP prior to formal study unblinding.

In addition, if the PPS population markedly differs from the ITT population, identical analyses for the PPS population will be performed.

Inferential results will be presented comparing EP-104IAR versus vehicle.

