### 3. STATISTICAL METHODOLOGY

#### 3.1 General Principles

All collected study data will be presented in listings. All derivations and statistical analyses will be performed using SAS® software Version 9.4 (or higher) or Phoenix® WinNonlin® Version 8.3 (or higher) (Certara USA, Inc., Princeton, NJ). Prior and concomitant medications/procedures will be coded using World Health Organization (WHO) Drug Dictionary Enhanced March 1, 2021 (or most recent version prior to data base lock). Adverse events will be coded using Medical Dictionary for Regulatory Activities (MedDRA) Version 24.0 (or most recent version prior to data base lock).

Unless stated otherwise, descriptive summaries for continuous variables will include n (number of subjects with non-missing results), mean, standard deviation (SD), median,  $Q_1$ ,  $Q_3$ , minimum, and maximum. For categorical variables, n and percent will be provided. Percentages will be calculated out of the number of subjects in the given sample with a non-missing result.

The primary means of efficacy data collection will be via an electronic patient-reported outcome (ePRO) device. Subjects will be provided with a hand-held device programmed to prompt the subject to record data as required throughout the study. The primary means of non-efficacy data collection will be via the electronic case report forms (eCRFs).

Summaries presented by collection day and/or by time point will be based on scheduled assessments as planned in the protocol except for all WOMAC data (See Section 4.1). Unscheduled assessments will be presented in listings and will not be included in the analyses except for: determination of baseline as described in Section 4.3, ACTH stimulation test summaries (See Section 4.4), and for the derivation of PK parameters.

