## 4. DATA HANDLING

### 4.1 Screening, Baseline, Pre-Dose, and Study Visits

Except for PK and WOMAC data, which will be analyzed at the actual sampling times, all other analyses will be presented based on the planned schedule of assessments in the protocol and recorded on the eCRFs and ePRO devices.

WOMAC pain post-baseline data (including subscale and associated questions) will be analyzed based on actual week from dosing per the mapping rules below:

Actual Week	Target Day	Study Day Range
Week 1	Day 8	7-13
Week 2	Day 15	14-20
Week 3	Day 22	21-27
Week 4	Day 29	28-34
Week 5	Day 36	35-41
Week 6	Day 43	42-48
Week 7	Day 50	49-55
Week 8	Day 57	56-62
Week 9	Day 64	63-69
Week 10	Day 71	70-76
Week 11	Day 78	77-83
Week 12	Day 85	84-90
Week 13	Day 92	91-97
Week 14	Day 99	98-104

Week 15	Day 106	105-111
Week 16	Day 113	112-118
Week 17	Day 120	119-125
Week 18	Day 127	126-132
Week 19	Day 134	133-139
Week 20	Day 141	140-146
Week 21	Day 148	147-153
Week 22	Day 155	154-160
Week 23	Day 162	161-164
Week 24	Day 169	165-174

WOMAC stiffness, WOMAC function, and WOMAC total post-baseline data (including subscales and associated questions) will be analyzed based actual week from dosing per the mapping rules below:

Actual Week	Target Day	Study Day Range
Week 4	Day 29	7-43
Week 8	Day 57	44-71
Week 12	Day 85	72-99
Week 16	Day 113	100-127
Week 20	Day 141	128-155
Week 24	Day 169	156-183

If more than one WOMAC data point is mapped to the same actual week, the one data point that is closest to the target day at the time of dosing will be used. Any data points that fall outside the windowing study day range will not be used.

Unless stated otherwise, baseline will be the last non-missing value, including unscheduled, prior to study drug administration. See Section 3.7 for the definition of baseline WOMAC pain. For efficacy data that are collected daily (NPRS scores, rescue medication usage, and physical activity levels), baseline is defined as the average of the available 7 days prior to dosing. Screening, when summarized, will be the last non-missing value, including unscheduled, that is prior to the day of study drug administration.

	EP-104IAR-201 Statistical Analysis Plan	Version: Final 1.0
	Date: 14-Jun-2023	Page 34 of 38

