#### 4.4 Unscheduled Data

Except for ACTH stimulation test results as described below, data obtained from unscheduled assessments (which also includes early exit visits) will only be considered for baseline determination; otherwise, unscheduled data will not be used in summary tables or included in the analyses. All unscheduled data will be presented in the listings.

ACTH stimulation test results will be mapped via the windowing rules in the below table. When more than one result for a subject occurs within one visit window, the worst result (i.e., Fail) will be mapped to that visit.

Visit (Mapped)	Target Day	Study Day Range
Screening		<1
Week 1	Day 3	1-9
Week 2	Day 15	10-22
Week 4	Day 29	23-43
Week 8	Day 57	44-71
Week 12	Day 85	72-106
Week 18	Day 127	107-148
Week 24	Day 169	149+

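### SAP 4.4 keeps early-exit efficacy scores out of the analyses without declaring it as a deviation; for PtGA and MDGA this is unambiguous, for WOMAC it contradicts SAP 3.1 and 4.1, and the likely effect is small

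*Protocol*

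**What the plan says.** **Protocol.** The synopsis (Statistical Methods) says change from baseline in WOMAC Pain is "fit to a mixed-effects for repeated measures model using all available data from the ITT population", with key secondary endpoints analysed by analogous methods. Section 11.7.1 describes the model input: "Change from individual pre-dose baseline will then be calculated for each post-dosing weekly assessment from Week 1 through Week 24". Sections 5.4 and 9.2.6 ask subjects who withdraw to complete the Visit 9 assessments (5.4 adds: where possible). Section 9.2.5.7 lists the WOMAC Index, PtGA and MDGA among them. The synopsis says of the combined End-of-Study or Early Exit visit: "Subjects will attend the site for final safety, PK and efficacy assessments".

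**SAP, excluding.** Section 4.4 states that "data obtained from unscheduled assessments (which also includes early exit visits) will only be considered for baseline determination" and that "otherwise, unscheduled data will not be used in summary tables or included in the analyses". ACTH stimulation tests are its only exception. Section 3.1 agrees: "Unscheduled assessments will be presented in listings and will not be included in the analyses except for: determination of baseline", followed by ACTH tests and PK derivation. No efficacy score is among the exceptions, apart from use as a baseline.

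**SAP, including.** Section 3.1 also takes all WOMAC data out of the rule that time-point summaries follow scheduled assessments, and refers to 4.1. There, WOMAC Pain "will be analyzed based on actual week from dosing per the mapping rules below", with a second table for Function, Stiffness and Total. Section 4.1 does not exclude a WOMAC score because it came from an exit visit.

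**Endpoints concerned.** SAP 3.8.1 makes WOMAC Function at Week 12 the first key secondary endpoint in a fixed testing order. SAP 3.8.2 analyses PtGA and MDGA at Weeks 4, 8, 12, 18 and 24 in the same way as the primary. SAP section 5, which lists departures from the protocol, does not mention early-exit data.

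**The concern.** The MMRM rests on missing at random (SAP 3.7): given the scores in the model, dropout must not depend on the scores that are missing. If a subject leaves because the knee is bad now, the exit score is what makes the departure predictable from observed data. Collecting that score and then removing it weakens the assumption.

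The exposure depends on how old the last retained score is. It is low for weekly scores and higher for scores collected every four to six weeks.

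There is also a reproducibility problem. Two programmers following the same SAP could build different Week 12 Function datasets, and the result of that test decides whether the later key secondary endpoints may be tested at all. Under Protocol 11.1 the SAP is to be final before unblinding, so the choice should not be left open until then.

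**Working it through.** **1. Planned size, for scale.** Inputs from Protocol 11.2 and SAP 3.3: difference 0.8, SD 2.2, two-sided 5%, power 80%, dropout 20%.
- n per arm = 2 × (1.960 + 0.842)² × 2.2² / 0.8² = 118.7, so 119. The plan says about 120, where power is 80.4%. This reproduces.
- 240 / (1 − 0.20) = 300 randomized. This also reproduces, and leaves up to 300 − 240 = 60 subjects who might have an exit visit.
- Standard error of a difference with 120 per arm: 2.2 × √(2/120) = 0.284 points.

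**2. Age of the last retained score if exit scores are dropped** (compliant subject, target days)

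| Score | Collection | Longest gap |
|---|---|---|
| WOMAC Pain | weekly at home | about 7 days |
| WOMAC Function, Stiffness | every 4 weeks | about 28 days |
| PtGA, MDGA | visits at Weeks 4, 8, 12, 18, 24 | 127 − 85 = 42 days; 169 − 127 = 42 days |

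**3. The two SAP rules applied to one subject.** Exit on Day 78 with a full WOMAC; last home Function score on Day 57.
- SAP 4.1: Day 78 lies in the Week 12 Function window (Days 72 to 99). The Day 57 score belongs to Week 8 (Days 44 to 71). The exit score is therefore the only Week 12 value and is used.
- SAP 4.4: the exit score is listed only, and Week 12 is missing.

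This is not a rare corner. The 4.1 windows run without a gap over Days 7 to 174 for Pain and Days 7 to 183 for Function, so almost any exit score could be mapped.

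**4. How often 4.1 would actually use an exit score.** SAP 4.1 keeps only the score closest to the target day in each window. Assume home scores fall on target days.
- Function, Week 12 window: exits on Days 72 to 84 (13 days) have no competitor; exits on Days 86 to 99 (14 days) lose to Day 85. About half are used.
- Pain, Week 2 window (Days 14 to 20, target Day 15): only a Day 14 exit adds a score; Days 16 to 20 lose to Day 15.

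**5. Effect on the Week 12 difference.** The documents give no dropout mechanism or correlations, so these are illustrations on assumed inputs. Both use a true difference of 0.8, SD 2.2 (the plan's figure for Pain, assumed also for Function), 100,000 subjects per arm, and dropout driven by the current score.
- *Simulation A:* 24 weekly scores; variance 55% between subjects, 30% AR(1) with correlation 0.85, 15% noise; 20% leaving by Week 24; log-odds of leaving up 0.3 to 0.8 per point; SAP 4.1 windows.
- *Simulation B:* 12 weekly or 3 four-weekly scores; correlation 0.4 + 0.6 × 0.7^lag or 0.6 + 0.4 × 0.8^lag; 12% leaving by Week 12; log-odds up 0.3 or 0.6 per point; exit score falls at a planned time.

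| | Exit scores kept | Dropped | Loss |
|---|---|---|---|
| A, four-weekly Function | 0.80 to 0.78 | 0.79 to 0.72 | 0.01 to 0.06 |
| A, weekly Pain | – | – | 0.00 to 0.02 |
| B, four-weekly | 0.797 to 0.811 | 0.775 to 0.804 | 0.007 to 0.026 |
| B, weekly | 0.784 to 0.818 | 0.765 to 0.815 | 0.003 to 0.019 |

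Monte Carlo error of each estimate is about 2.2 × √(2/100,000) = 0.01. Losses in B compare the same simulated subjects. In standard errors, 0.06 / 0.284 = 0.21 and 0.026 / 0.284 = 0.09 for Function; 0.02 / 0.284 = 0.07 for Pain.

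**The case against.** **For WOMAC, 4.4 may not mean what it says.** SAP 3.1 carves WOMAC out, 4.1 maps it by actual day, and the safety sections (SAP 3.8.4) present Week 24 or Early Termination results that 4.4 would bar. This stands: for WOMAC the documents show an unresolved contradiction, not a settled exclusion. It does not help PtGA and MDGA, which the 4.1 windows do not cover.

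**The primary endpoint keeps its data.** A reader might infer that the score nearest each leaver's departure is lost from the primary analysis. The documents do not support that. Home Pain entries are weekly, 4.4 does not remove them, and Protocol 11.7.1 builds the model on those weekly records. This stands.

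**The multiple imputation in SAP 3.7 already tests missing at random.** Partly. EP-104IAR subjects who leave for lack of efficacy are imputed as if on vehicle. That addresses this kind of dropout in the active arm. For a vehicle leaver the rule is still imputation from the subject's own arm. In both arms it works from the retained scores, so it does not recover excluded ones.

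**The effect is small, and it shrinks the treatment difference.** This stands. In these simulations the loss does not favour the drug, and its upper end needs a steep link between score and leaving (log-odds 0.8, an odds ratio of about 2.2 per point).

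**Including exit scores is not a full cure.** Leavers attend only if possible, and step 4 shows that 4.1 would leave many exit scores unused. This stands and limits what the fix can promise.

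**PtGA and MDGA are outside the testing hierarchy.** True; for them the issue is lost information, not the error rate.

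**Conclusion.** The point holds in a limited form. SAP 4.4, supported by 3.1, sets aside efficacy scores that the protocol takes care to collect. It departs from the protocol's all-available-data rule, and section 5 does not say so. For PtGA and MDGA the exclusion is clear. For WOMAC the SAP gives two incompatible instructions, which matters most for Function at Week 12.

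The expected numerical effect is modest: about 0.01 to 0.06 points for four-weekly Function and 0.00 to 0.02 for weekly Pain, against a standard error of about 0.28, towards a smaller difference. These figures rest on assumed dropout mechanisms and correlations and on a Pain SD applied to Function. No simulation was run for PtGA or MDGA.

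Two stronger conclusions are not supported: that every early-exit WOMAC score is certainly excluded, and that the primary result is materially at risk. The reason to act is that the rule is contradictory, undeclared and easy to settle before unblinding.

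**What to change.** - **SAP 3.1 and 4.4:** add early-exit efficacy scores to the listed exceptions.
- **WOMAC Pain, Function and Stiffness:** map early-exit scores by the 4.1 day windows. Accept that, under the existing closest-to-target rule, an exit score is used only where no closer score exists in that window.
- **PtGA and MDGA:** map early-exit scores to the analysed visits only (Weeks 4, 8, 12, 18 and 24), by prespecified day windows with a bounded Week 24 window. Do not reuse the ACTH table in 4.4 unchanged. It sends Days 1 to 9 and 10 to 22 to Weeks 1 and 2, which are not analysed for these scores, and everything from Day 149 to Week 24, that is, from 169 − 149 = 20 days before target.
- **SAP section 5:** list any early-exit exclusion that remains.

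Cost: a few sentences and one short window table in a SAP revision before unblinding, plus the matching programming. The data are already collected; no extra subjects or visits are needed, and the sample size is unaffected.

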Table 2	Topical Corticosteroid Potency Chart.....
Table 3	Medications Permitted at Stable Doses.....
Table 4	Prohibited Drugs and Therapies.....
Table 5	Kellgren-Lawrence Grading Scale Criteria
Table 6	Criteria for Selecting the Index knee in Subjects with a Diagnosis (or Symptoms) of Bilateral Knee OA at Screening
Table 7	AE Severity/Intensity Criteria.....
Table 8	AE Causal Relationship Categorization.....

LIST OF FIGURES

	Page
Figure 1 Visit Overview	40
Figure 2 Triggers for ACTH Stimulation Testing.....	71

LIST OF ABBREVIATIONS

ACR	American College of Rheumatology
ACTH	Adrenocorticotropic hormone
ADR	Adverse drug reaction
AE	Adverse event
AI	Adrenal insufficiency
ALT	Alanine aminotransferase
AST	Aspartate aminotransferase
AUC	Area under the curve
BMI	Body mass index
BP	Blood pressure
CFB	Change from baseline
CKD-EPI	Chronic Kidney Disease Epidemiology Collaboration
Cmax	Maximum concentration
Conmed	Concomitant medication
CRA	Clinical research associate (also referred to as a monitor/site monitor)
CRO	Contract Research Organization
Css	Average concentration at steady state
DCE-MRI	Dynamic Contrast Enhanced MRI
eCRF	Electronic case report form
EDC	Electronic data capture
eGFR	Estimated Glomerular Filtration Rate
ePRO	Electronic patient-reported outcome
EP-104IAR	Long-Acting Fluticasone Propionate for Intra-Articular Injection
FAS	Full analysis set
FP	Fluticasone propionate
GBCA	Gadolinium Based Contrast Agent
GCP	Good Clinical Practice
GLP	Good Laboratory Practice
HbA1c	Hemoglobin A1c
HPA	Hypothalamic pituitary adrenal axis
IA	Intra-articular
ICF	Informed consent form
ICH	International Council for Harmonisation
ID	Identification
IEC	Independent Ethics Committee
IMP	Investigational Medicinal Product (also referred to as study-drug)
IP	Intraperitoneal
IRB	Institutional Review Board
IRT	Interactive response technology

ITT	Intention-to-treat
IV	Intravenous
MDGA	Physician's Global Assessment of Arthritis
MedDRA	Medical Dictionary for Regulatory Activities
MMRM	Mixed-effects model for repeated measures
MRI	Magnetic resonance imaging
NIMP	Non-investigational medicinal product
NOAEL	No observed adverse effect level
NPRS	Numeric Pain Rating Scale
NRS	Numeric rating scale
NSAID	Non-steroidal anti-inflammatory drug
OA	Osteoarthritis
OMERACT-	Outcome Measures in Rheumatology-Osteoarthritis Research
OARSI	Society International
PK	Pharmacokinetic(s)
PPS	Per-protocol analysis set
PtGA	Patient's Global Assessment of Arthritis
PtPain	Patient pain scores (11-point numerical rating scale)
PVA	Polyvinyl alcohol
SAE	Serious adverse event
SAP	Statistical Analysis Plan
SC	Subcutaneous
SF-36	Short Form 36 Health Survey
SRC	Safety Review Committee
SRM	Safety Review Meeting
SUSAR	Suspected Unexpected Serious Adverse Reaction
TCA	Triamcinolone acetonide
TEAE	Treatment-emergent adverse event
TK	Toxicokinetic
ULN	Upper limit of normal
US	United States
WBC	White blood cell
WHO-Drug	World Health Organization drug dictionary
WMA	World Medical Association
WOMAC	Western Ontario and McMaster Universities Osteoarthritis Index

